#### 3. Abstract.

Modulation of a patient's diet, specifically via short-term dietary protein restriction, can impact changes in cell energetics and dampen the normal subclinical inflammatory state. These changes can provide benchmarks for future research focused on using nutritional interventions aimed at improving the probability of a successful outcome following open aortic aneurysm surgery. We will conduct a short term dietary restriction study to characterize these changes in a normal control cohort. Knowledge gained from these experiments will be used in comparison to patients undergoing major surgery during a future study, as well as to identify the optimal time points for sample collection in our surgical population. These changes will be characterized by looking at inflammatory cells in the blood, proteins excreted in the urine, changes in microbiome signature of the stool and oral mucosal bacteria, as well as changes in skeletal muscle energetics derived from small biopsies.

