## 4. Background

Our group is interested in developing a robust prospective translational research effort that focuses on patients undergoing open abdominal aortic aneurysm (AAA) repair since they have some of the highest rates of postoperative morbidity and mortality compared to other elective non-cardiac surgical patients. The underlying biologic basis of frailty in AAA patients that makes some subjects more vulnerable to postoperative complications is poorly understood. Short-term dietary protein restriction (stDPR) is a cost-effective, easily applied intervention that has strong pre-clinical data supporting efficacy in reducing surgical stress responses. Moreover, recent data supports the feasibility and safety of using stDPR to reduce adverse outcomes after cardiac surgery. These seminal observations offer a unique opportunity for application to other high-risk surgical patient populations known to have significant post-operative adverse event rates. Before initiating a clinical trial in AAA subjects, we need to characterize observations in healthy control, non-surgical subjects who are exposed to stDPR. Therefore, this pilot study is

designed to explore the ability of stDPR to impact the sub-clinical inflammatory milieu and skeletal muscle bioenergetics in a cohort of healthy, non-surgical patients.

**5. Aim**: Examine the baseline and early changes in muscle energetics, microbiome, and cell-mediated inflammation in healthy control patients receiving short-term dietary protein restriction.

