Microbiome Sample Processing: Three stool samples will be collected on Day 0, Day 4, and Day 7. Stool collection kits and instructions will be given to patients at their screening visit. Patients will collect their feces in a toilet insert (similar to an upside down hat) and will take a walnut sized scoop of this feces using a provided tube/scooper and insert it in the collection container and bag. Stool samples may be collected at home within 24 hours of the clinic visit or during clinic visits on Day 0, 4 and 7. In addition, a swab of cheek saliva will be collected using a sterile swab and placed into a provided sterile tube. DNA will be extracted from these samples using DNeasy PowerLyzer PowerSoil Kit (Qiagen) and will be quantified using spectrophotometry. Amplification of 16S rRNA will be performed to create amplicons, after which PCR will be used to add adapters and dual-index barcodes to the amplicon target. These libraries will be pooled together for sequencing by Illumina MiSeq. Reads will be assigned to operational taxonomic units, which will enable us to identify phyla, classes, families, and genera in each sample. The MiSeq run output is approximately >20 million reads and can generate sufficient reads for metagenomic surveys.

Operational taxonomic units (OTUs) for bacterial species at each time point will be determined for all patients. Both alpha-diversity (overall diversity) and beta-diversity (composition of species) measurements will be obtained from these OTUs. Mann-Whitney tests will be used to compare alpha diversity in patients who developed post-operative complications to those who did not. One-way analysis of variation (ANOVA) or Kruskal-Wallis tests will similarly be conducted to compare beta-diversity  $^{21}$ . Heatmaps with clustering for relative abundance of species at the genus level will be created for all samples and pairwise differences between preoperative and post-operative samples will be identified. The response will be measured as a change from baseline, and the baseline response will be included as a covariate in the subsequent multivariate analysis. In addition to this, we will perform principal component analysis (PCA) to create a mixed multivariate model with the intent of combining laboratory values for IL-10, LXA4, TNF- $\alpha$ , and annexin-1 with OTUs.

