# Subject Enrollment

We anticipate enrolling 10 patients for up to a year following study initiation. Patients who express interest in learning more about the study will meet with a member of the study staff who will describe the study, review the informed consent form, give them a copy of the informed consent to read and answer any questions. Potential participants will be allowed to take a copy of the consent form, as well as written information about the study if they so desire. When possible, signing of the consent shall occur at least one day prior to diet initiation to allow adequate time for patient to make consideration without any stress. Any questions will be answered by the Principal Investigator or other study team members.

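### Beta-diversity is assigned a one-way ANOVA or Kruskal-Wallis test, but the comparison that serves the aim is across study days in the same 10 subjects, where a test with no subject term can lose most of its power

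*Protocol*

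**What the plan says.** Section 6 of the protocol (Research Plan, Microbiome Sample Processing) gives the only named test for beta-diversity: "One-way analysis of variation (ANOVA) or Kruskal-Wallis tests will similarly be conducted to compare beta-diversity". The preceding sentence uses Mann-Whitney tests to "compare alpha diversity in patients who developed post-operative complications to those who did not", and the beta-diversity sentence is worded as its counterpart.

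The data come from one cohort with no arms. On stool: "Three stool samples will be collected on Day 0, Day 4, and Day 7". The time-point table in the same section adds cheek swabs on Days 0, 2, 4, 7 and 14. On size, Subject Enrollment states: "We anticipate enrolling 10 patients for up to a year following study initiation". Section 4 and Subject Selection describe healthy, non-surgical volunteers.

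Section 5 sets the aim: "Examine the baseline and early changes in muscle energetics, microbiome, and cell-mediated inflammation in healthy control patients". The Abstract adds that the results should help "identify the optimal time points for sample collection in our surgical population".

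Later in the microbiome paragraph comes this: "The response will be measured as a change from baseline". It is tied to a subsequent multivariate analysis, not to the beta-diversity test.

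**The concern.** The grouping that the beta-diversity test leans on cannot arise, since nobody in this study has surgery. Once it is removed, the aim leaves study day as the factor, with every subject measured on every day. One-way ANOVA and Kruskal-Wallis assume independent groups and carry no subject term, so they ignore that pairing.

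What follows depends on the unit tested, which the protocol does not state.

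- **One score per sample** (for example, an ordination axis). Stable differences between people stay in the error term. The test does not produce false positives, but it loses power.
- **Pairwise distances within each day.** Each sample enters many distances, so the values are not independent and type I error is inflated. The test also compares how spread out subjects are on each day. A shift shared by all subjects is not its target.

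The microbiome is one of three domains in the aim, and the pilot is meant to supply benchmarks and inform sampling times for the surgical study. A consistent diet effect could be missed or, if distances are tested, a spurious difference reported.

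**Working it through.** The protocol states no power, alpha, effect size, variance or distance metric, so it has no figure to reproduce. From the documents: 10 subjects; 3 stool days; 5 swab days; a test without a subject term. Assumed: alpha 0.05 and an intra-subject correlation (ICC) from 0 to 0.9.

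**A. One score per sample**

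Model: score = day mean + subject effect (variance ICC) + residual (variance 1 − ICC), so total variance is 1. Day 0 has mean 0 and every later day has mean δ. In residual SD units, δ is set so that the subject-blocked F test has 80% power:

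- 3 days: δ = 1.31; noncentrality = 10 × (2/3) × 1.31² = 11.44; F on 2 and 18 df; power 80%.
- 5 days: δ = 1.30; noncentrality = 10 × (4/5) × 1.30² = 13.52; F on 4 and 36 df; power 80%.

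With no effect, the between-day mean square has expectation 1 − ICC, because subject effects cancel across days. The one-way error mean square has expectation ICC + (1 − ICC) = 1. The F ratio is therefore centred near 1 − ICC instead of 1, for example near 0.3 at ICC 0.7. That is why the test becomes too conservative. Simulation (100,000 runs):

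| ICC | 0 | 0.3 | 0.5 | 0.7 | 0.9 |
|---|---|---|---|---|---|
| Blocked F test, power | 80% | 80% | 80% | 80% | 80% |
| One-way ANOVA, power, 3 days | 82% | 67% | 47% | 20% | 1% |
| One-way ANOVA, power, 5 days | 81% | 60% | 37% | 11% | 0.3% |
| One-way ANOVA, type I error, 3 days | 5.0% | 1.7% | 0.6% | 0.1% | 0% |

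A different effect pattern gives the same picture. With a shift of 1.5 within-subject SD at Day 4, half of it remaining at Day 7, the blocked test has about 79% power at every ICC. One-way ANOVA has 65%, 47%, 20% and 1% at ICC 0.3, 0.5, 0.7 and 0.9, and Kruskal-Wallis has 61%, 42%, 18% and 1%. With a 1.0 SD shift the figures are 29% against 44% at ICC 0.3 and 15% against 43% at ICC 0.5.

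**B. Pairwise distances within each day**

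Ten samples give 10 × 9 / 2 = 45 distances per day, and each sample appears in 9 of them. Assumed community: 50 taxa, taxon SD 1.5, log-abundance total variance 1.0, 10,000 reads, Bray-Curtis distances. The shift is ±0.5 log on all taxa at every later day. There were 199 permutations and 1,000 simulated stool studies per cell:

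| ICC | 0 | 0.3 | 0.5 | 0.7 | 0.9 |
|---|---|---|---|---|---|
| Kruskal-Wallis on distances, no effect | 50% | 48% | 44% | 31% | 7% |
| Kruskal-Wallis on distances, shift | 53% | 48% | 45% | 30% | 14% |
| PERMANOVA within subject, no effect | 6% | 5% | 5% | 6% | 5% |
| PERMANOVA within subject, shift | 52% | 68% | 82% | 95% | 99.8% |

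Repeat runs of the Kruskal-Wallis cell at ICC 0.7 with shift ranged from 30% to 42%; the reading is the same. Kruskal-Wallis rejects about as often with the shift as without it up to ICC 0.7, so a rejection says little about a diet effect. The inflation is greatest at ICC 0 and falls as ICC rises, so it comes from reuse of samples, not from repeated subjects. Over five swab days with no effect, Kruskal-Wallis rejects 67%, 59%, 46% and 10% at ICC 0.3, 0.5, 0.7 and 0.9.

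PERMANOVA power depends on the assumed shift. In a second set of scenarios (40 genera, 10 of them shifted, half of the shift left at Day 7, ICC 0.5 to 0.88) it was 16% to 54% with permutation within subject and 0% to 1% with free permutation. The gain from keeping the pairing does not depend on the first choice of settings.

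**The case against.** The strongest objection is that the protocol nowhere says beta-diversity will be compared across days by a one-way test. Read literally, the test compares complication groups, and with one value per subject an independent-groups test would suit that. The root error is then the grouping carried over from a surgical study, and the day comparison is inferred. This is true as far as it goes. But no other between-subject grouping is defined, and the planned comparison with surgical patients belongs to a future study. Deleting the complication groups alone would leave a one-way test on repeated samples.

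Second, the same paragraph mentions pairwise differences between pre- and post-operative samples, change from baseline and a mixed multivariate model, which suggests that paired change was in mind. None of these is tied to the beta-diversity test, so none gives it a subject term.

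Third, metric and unit are commonly left to the SAP, so the distance analysis is one possible reading only. That is fair, and it is why both readings are shown. The fault is that the protocol names an unsuited test, not that it omits detail.

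Fourth, the size depends on an ICC that the protocol does not give. This stands: nothing is lost at ICC 0, and at 0.3 the loss is modest (67% against 80%). In the three-day score model, most of the power is lost only above about 0.5.

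Finally, this is an exploratory pilot and no decision hangs on the p-value. That limits the weight of the point but does not make the test suitable.

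**Conclusion.** The concern holds. As written, the beta-diversity test either cannot be run, because its groups do not exist, or is an independent-groups test applied to repeated samples from 10 people. In the second case a per-sample score analysis falls from 80% power to between 67% and 1% over ICC 0.3 to 0.9 (three stool days). An analysis of within-day distances has false-positive rates of 48% down to 7% over the same range and does not target a common shift. These sizes rest on the assumed alpha, ICC, effect pattern and community model. The lack of a subject term does not depend on them. The consequence is a misleading pilot result, not a wrong trial decision, so this is a change that should be made rather than one that must be. Confidence is medium, because study day as the intended factor is inferred from the aim.

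**What to change.** Replace the beta-diversity sentence, together with the complication grouping it leans on. Suggested wording:

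> Beta-diversity (Bray-Curtis) will be compared between Days 0, 4 and 7 by PERMANOVA with permutations restricted within subject, with contrasts of Day 4 and Day 7 against Day 0 and a check of within-day dispersion. Cheek swabs will be analysed likewise over Days 0, 2, 4, 7 and 14.

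A paired analysis of each subject's change, or a subject-blocked model on a per-sample score, would also serve. Whichever is chosen, the protocol should name the unit of analysis and study day as the factor.

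Ten subjects are enough for a valid test. A two-day contrast has 2^10 = 1,024 within-subject relabellings. Swapping every label gives the same statistic, so the smallest p-value is 2/1,024, about 0.002.

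The cost is a rewording. Standard free software does the analysis, and no samples, visits or subjects are added.

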#### 6. Research Plan

Overview: Using targeted assays of mitochondrial energetics, 10X genomics, and the microbiome, we will assess changes in skeletal muscle bioenergetics and the leukocyte transcriptome induced by a prescribed 96-hour protein restriction diet, tracking the impact of these changes on the dynamic response patterns of these parameters in healthy control patients.

Study Time points Summary							
	Days -7 to -1	Baseline/Day 0	Day 2	Day 4	Day 7	Day 14	
Consent	x						
Paffenbarger IQ	х						
IPR Study IQ		х	х	х	х	х	
Stool Kit Distribution	x	х	х				
Diet Kit Distribution		х	х				
Blood		х	х	х	х	х	
Urine		х	х	х	х	х	
Feces		х		х	х		
Cheek Swab		х	х	х	х	Х	
Muscle Biopsy		х		х	х		
Meal Logger				Days 5 thru 14			

Health Questionnaires: We will collect height and weight information to be utilized in the diet equation, as well as 2 questionnaires. The first is a physical activity Paffenbarger questionnaire which is used for the diet equation (see below) and an IPR study questionnaire to track energy level, mental awareness, and digestive issues.

Diet Modification: Subjects will follow a 4 day protein restricted diet using Scandishake® mixed with almond milk which will be provided. They may also drink water. No food, other beverages, or alcohol may be consumed. The amount of diet to be consumed will be calculated for each patient based upon resting energy expenditures plus additional energy needs using the Paffenberger IQ. REE = 9.99 x weight (KG) + 6.25 x height (cm) - 4.92 x age + 166 x sex (males, 1; females, 0) - 161. Patients will receive the study diet (ScandiShake® [any of 4 flavors] mixed

with almond milk), calculated individually for a total daily volume to achieve 30% caloric restriction and 70% protein restriction. These will be consumed by the study subjects at home in an unrestricted manner, in that they may be consumed at any point of time in the day.

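### Using baseline as a covariate of its own change adjusts no group contrast in this one-group microbiome analysis, and the resulting coefficients can mislead if read as the diet-period change

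*Protocol*

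**What the plan says.** The sentence at issue is in section 6 (Research Plan), under Microbiome Sample Processing. It says the response will be "measured as a change from baseline, and the baseline response will be included as a covariate in the subsequent multivariate analysis". It does not say whether baseline is centred, which coefficient carries the result, or what else is in the model.

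The design has a single arm. The Aim statement after section 4 (Background) concerns changes "in healthy control patients receiving short-term dietary protein restriction", and under Diet Modification every participant gets the same treatment: "Subjects will follow a 4 day protein restricted diet using Scandishake® mixed with almond milk which will be provided". Subject Enrollment gives the size: "We anticipate enrolling 10 patients".

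On sampling, "Three stool samples will be collected on Day 0, Day 4, and Day 7"; the time-points table adds cheek swabs on Days 0, 2, 4, 7 and 14. The same microbiome paragraph does name a group comparison, "Mann-Whitney tests will be used to compare alpha diversity in patients who developed post-operative complications to those who did not", but this cohort has no surgery, so those groups cannot be formed.

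**The concern.** Adjusting a change score for its baseline is a sound way to sharpen a comparison between groups. With one group there is nothing to sharpen. What remains is a regression of change on baseline with two coefficients, and neither is a safe summary of what happened to the microbiome during the diet:

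- The intercept, with baseline entered as recorded, is an extrapolation to a baseline of zero.
- The slope is negative through regression to the mean whenever the within-person correlation is below 1, whether or not the diet does anything.

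The natural remedy, centring baseline at the sample mean, repairs the intercept as a point estimate but leaves its usual standard error too small for inference about the population mean change. The Aim is to describe early changes, and the Abstract says the results will serve as a comparison for future surgical patients and help choose sampling times. For the microbiome part of that aim, mean change is the quantity that has to be estimated and given an honest interval.

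**Working it through.** **Inputs from the protocol.** One group; n = 10; response = change from baseline; covariate = baseline. The protocol gives no planned figure for this analysis, so there is none to reproduce.

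**Assumptions not in the protocol.** Baseline B and follow-up F are bivariate normal with equal SD (set to 1) and within-person correlation rho; one follow-up and one predictor; true mean change δ, with δ = 0 for rejection rates; two-sided 5% level. Since rho is not given, a range is shown.

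**Algebra.** Let D = F − B.

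- Slope: Cov(D, B) / Var(B) = rho − 1.
- Uncentred intercept: expectation δ + (1 − rho) × baseline mean.
- Sample-mean-centred intercept: exactly the observed mean of D, hence unbiased for δ.
- Variance of D: 2(1 − rho). Residual variance of D given B: 1 − rho².
- Ratio of the centred model's standard error to the correct one: sqrt[(1 − rho²) / (2(1 − rho))] = sqrt((1 + rho)/2).

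**Centred intercept, size of the test.** Under these assumptions the mean change is independent of the residual sum of squares (8 df). The rejection rate with no true change is therefore P(|t₈| > 2.306 × sqrt((1 + rho)/2)).

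| rho | SE ratio | Effective cut-off | Rejection rate |
|---|---|---|---|
| 0.3 | 0.806 | 1.859 | 10.0% |
| 0.5 | 0.866 | 1.997 | 8.1% |
| 0.8 | 0.949 | 2.188 | 6.0% |
| 0.9 | 0.975 | 2.248 | 5.5% |

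Simulation of 200,000 trials at rho = 0.3 / 0.5 / 0.8 gives 9.9% / 8.1% / 5.9%. The plain paired t-test gives 5.0% / 5.1% / 4.9% on the same data.

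**Interval width for mean change (SD units).** At rho = 0.5 the centred model's half-width is 0.612, against 0.695 for the paired t, and its coverage is 91.9%. At rho = 0.8 the half-widths are 0.424 and 0.440, with coverage 94.0%.

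**Uncentred intercept.** With the baseline mean 5 SD above zero and no true change, the expected intercept is (1 − 0.5) × 5 = 2.5 SD at rho = 0.5 and (1 − 0.8) × 5 = 1.0 SD at rho = 0.8. Its test rejects about 41–47% / 28–32% / 13–14% of the time at rho = 0.3 / 0.5 / 0.8, for baseline means 2 to 8 SD from zero. Its interval is wide, not narrow: half-width 2.49 SD at rho = 0.8. The fault here is the target, not the precision.

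**Slope.** Its expectation is −0.7 / −0.5 / −0.2 at rho = 0.3 / 0.5 / 0.8, and it is significant at 5% in about 47% / 33% / 14% of trials with no diet effect. Centring does not alter it.

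**The case against.** The strongest reply is that the protocol never says the intercept is the diet effect or that the slope will be interpreted. Centring, model form and standard errors are usually settled in a statistical analysis plan, which is not at hand. That stands as a limit: the harm depends on how the model is used. It does not remove the point, because the text commits to a method and does not merely leave a gap, and that method has no group contrast to serve here.

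A reader might also infer that the model gives a misleading intercept, a spurious slope and too-narrow intervals all at once, even with centring. The documents and the arithmetic do not support that. No single parameterisation has all three faults:

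- Sample-mean centring makes the intercept exactly the mean change.
- The uncentred interval is far wider than the paired one.
- Centring at a known population mean gives 95% coverage.
- The slope's own interval correctly covers rho − 1; only reading it as a diet effect is wrong.

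Nor does the sentence reach the muscle or transcriptome analyses. It belongs to the microbiome paragraph.

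It is also fair to say that this wording fits a surgical cohort, where comparing patients with and without complications would justify the covariate, and that correcting that mismatch would touch this sentence too. But removing the surgical groups alone would leave the covariate in place, so it still needs its own correction.

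Finally, the calculation uses one follow-up and one predictor, whereas stool has two follow-ups, cheek swabs have four, and the planned model may hold more terms. The figures illustrate the mechanism and do not predict the trial's exact error rate.

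**Conclusion.** The point holds as a limited correction to the microbiome analysis. In one group the baseline covariate adjusts no contrast, and the mean change is better estimated without it. The only defect that survives sample-mean centring of the intercept is its standard error. That is about 19% too small at rho = 0.3, 13% at 0.5 and 5% at 0.8, so a nominal 5% test rejects about 10%, 8% and 6%. At high correlation the loss is slight. The uncentred intercept and the slope can mislead much more, but only if reported as the diet-period change or as dependence of the effect on baseline, which the protocol does not say it will do. All sizes rest on assumed correlations, equal SDs and normality; the uncentred figures also assume a baseline mean.

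**What to change.** For the microbiome measures, name mean change from Day 0 as the estimand and drop baseline as a covariate of its own change. Estimate it in either of two ways:

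- paired contrasts (paired t or Wilcoxon signed-rank); or
- a repeated-measures model in which Day 0 is one of the outcomes and day is a categorical effect.

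Use only the days sampled: Days 4 and 7 against Day 0 for stool; Days 2, 4, 7 and 14 against Day 0 for cheek swabs. If a change-on-baseline slope is shown at all, state that it is expected to be negative without any diet effect and is not evidence that the effect depends on baseline.

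The cost is a change of analysis wording. No new data, visits or participants are needed.
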